Randomization will be performed after the patient has agreed to participate, discussed the study, and signed the informed consent form. Using a random number generator, patients will be randomized in a 1:1 ratio into either the control (no abdominal binder) or the treatment (abdominal binder) group. Envelopes will be used to mask allocation to either the treatment group (abdominal binder) or the control group (no abdominal binder). Envelopes will be opened and allocation revealed after the conclusion of the procedure.

Risks:

There is a potential risk of breech of confidential information.

There is a risk of increased abdominal discomfort and skin irritation with abdominal binder use.

Benefits:

The potential benefit to subjects enrolled in the study includes improved pain control and quicker return to pre-surgery functioning. There is no financial benefit to participation. Although the patient may benefit from improved postoperative pain control and earlier ambulation, there may not be a direct benefit to study participation.

Day of Surgical Procedure

The surgical procedure will be performed using the standard procedures established in MacDonald Women's Hospital by an attending physician with a fellow and a resident. No deviation or alteration of the surgical procedure is needed to complete this study. Patients enrolled in the study to the experimental arm will have an abdominal binder ordered with their standard post-operative orders those enrolled in the control arm will not have a binder ordered.

Postoperatively, the patient will be encouraged to wear the abdominal binder continuously throughout their hospital stay, however if they wish to remove the binder for a period of time they will be able to do so. Patients will have standard narcotic and non-narcotic pain medications ordered for use after surgery. Patients will be given a Visual Analog Scale (VAS) to rate their pain at four time points during the study; pre-operatively, immediately (at 1 hour) post-operatively in the recovery area, twelve hours post-operation, and on the morning of post-operative day one. Additionally, the post-operative day number and exact time of the patient's first ambulation will be recorded.

After discharge home:

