The Principal Investigator will notify the local review committee, i.e., the Institutional Review Board (IRB) as per local IRB requirements. Documentation of these reports will be kept in the site's study files

Stopping Criteria

The trial can be stopped at any point if safety concerns arise.

Statistical Considerations:

Based on retrospective data, a power analysis was performed and it was determined that a total of 88 patients (44 in each arm) would be required to achieve a power of 80% with an alpha error of 0.05 in order to detect a true difference in opioid (morphine equivalent) use between the groups. When an appropriately sized group is obtained, we will analyze the prospective data for difference in morphine use via univariate analysis, by either a t-test or Mann-Whitney U depending upon the distribution. Additionally, data will be evaluated with descriptive statistics, including means, medians, standard deviations, and ranges.

Study Parameters:

Age

Body Mass Index (BMI)

Medical Co-Morbidities

Past Surgical History

Type of procedure

Indication for procedure

Length of procedure

Post-operative complications

Pain assessment using Visual Analogue Scale (preoperatively, immediately after surgery in PACU, 12 hours postoperatively, and 24 hours postoperatively (POD#1)

Time to first ambulation

Total postoperative narcotic usage (Morphine equivalents, will be calculated based on inpatient usage and outpatient usage. Outpatient usage will be determined by calling the patient on POD#7 and asking how many narcotic pills they have remaining and then comparing that to what the EMR shows the narcotic prescription dispense number.)

Data / Record Keeping

Paper or written study data will have a study number rather than PHI. Subsequently, collected study data will be managed using REDCap (Research Electronic Data Capture) electronic data capture tools hosted at Case Western Reserve University.

REDCap is a secure, web-based application designed to support data capture for research studies, providing: 1) an intuitive interface for validated data entry; 2) audit trails for tracking data manipulation and export procedures; 3) automated export procedures for seamless data downloads to common statistical packages; and 4) procedures for importing data from external sources.

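### Anaesthetic and analgesic treatment given in theatre is not among the recorded parameters and has no pre-specified use, although the late envelope opening makes it a valid pre-allocation covariate

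*Combined protocol and SAP*

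**What the plan says.** All references are to the combined protocol and SAP.

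- **Study Parameters** lists age, BMI, comorbidities, surgical history, the type of, indication for and length of procedure, complications, VAS pain, time to first ambulation and "Total postoperative narcotic usage (Morphine equivalents, will be calculated based on inpatient usage and outpatient usage". No item concerns anaesthetic technique, blocks, wound infiltration or opioid given in theatre.
- **Day of Surgical Procedure** describes the operation and the post-operative analgesic orders only as standard, and sets no theatre regimen. VAS is taken before surgery and then "immediately (at 1 hour) post-operatively in the recovery area, twelve hours post-operation, and on the morning of post-operative day one". The time of first ambulation is recorded.
- **Randomization**: "patients will be randomized in a 1:1 ratio into either the control (no abdominal binder) or the treatment (abdominal binder) group", with no stratification mentioned. Randomization follows consent, but "Envelopes will be opened and allocation revealed after the conclusion of the procedure".
- **Statistical Considerations** sets the sample size at 88, or 44 per arm, on the basis of unnamed retrospective data, for "a power of 80% with an alpha error of 0.05". The target is morphine-equivalent opioid use, with no difference or SD stated. Opioid use is compared by t-test or Mann-Whitney test according to its distribution, without covariates. No test is named for VAS or first ambulation.
- **After discharge home** plans a later review of the electronic record. **Data / Record Keeping** keeps identifiers until analysis is complete, so that further information can be looked up if needed.

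**The concern.** The trial admits any scheduled pelvic surgery with an overnight stay and names eight facilities, so theatre anaesthesia and analgesia may well vary between patients. A block or long-acting analgesic given in theatre can act for hours, which is when the 1-hour and 12-hour VAS, first ambulation and early inpatient opioid doses are measured. With 44 per arm, a chance excess of blocks in one arm could imitate or mask part of a binder effect on these outcomes.

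The design makes this variable unusually safe to use. Since the arm is not known until the operation is over, theatre treatment is a pre-allocation characteristic in the sense that matters for adjustment. Post-operative analgesia is not, because knowledge of the arm can influence it. As written, the plan commits neither to showing readers the balance of theatre treatment nor to using it.

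**Working it through.** **Inputs from the documents.** 44 per arm, power 80%, alpha 0.05 (sidedness not stated; two-sided assumed). The difference and SD behind the sample size are not given, so 88 cannot be reproduced forward.

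**Inputs assumed.** Share of patients with a block, q = 10% to 50%. Effect of a block on the outcome, e = 0.4 to 1.0 within-group SD. The documents support neither figure.

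**1. Detectable difference, solved backwards.** Normal approximation: d = sqrt(2/44) × (1.960 + 0.842) = 0.2132 × 2.802 = 0.597. The t-test gives 0.604. As a check, d = 0.60 requires 44 per arm, so 88 is consistent with d of about 0.6. This applies to opioid use; no power target is stated for VAS or ambulation.

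**2. Chance imbalance in block use (95% limit).** 1.96 × sqrt(2q(1−q)/44).

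**3. Shift in the arm difference at that limit, in total SDs.** Imbalance × e / sqrt(1 + q(1−q)e²).

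**4. Variance explained.** R² = q(1−q)e² / (1 + q(1−q)e²).

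**5. Value of adjustment.** Equivalent total N = 88/(1−R²). Power is that of a t-test with 44 per arm at d = 0.604/sqrt(1−R²).

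| q | e | Imbalance limit (points) | Shift at limit (SD) | Shift as share of 0.604 | R² | Equivalent N | Power |
|---|---|---|---|---|---|---|---|
| 10% | 0.4 | 12.5 | 0.05 | 8% | 0.014 | 89 | 80.6% |
| 20% | 0.4 | 16.7 | 0.07 | 11% | 0.025 | 90 | 81% |
| 30% | 0.7 | 19.1 | 0.13 | 21% | 0.093 | 97 | 84% |
| 50% | 1.0 | 20.9 | 0.19 | 31% | 0.20 | 110 | 88% |

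Worked example, last row: q(1−q)e² = 0.25; R² = 0.25/1.25 = 0.20; N = 88/0.80 = 110; d = 0.604/sqrt(0.80) = 0.675. The imbalance limit is 1.96 × sqrt(0.5/44) = 0.209, and the shift is 0.209 × 1.0/sqrt(1.25) = 0.187.

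These shifts are the edge of the 95% range. One standard deviation of the shift is the tabulated figure divided by 1.96: 0.05/1.96 = 0.025 SD in the first row and 0.187/1.96 = 0.095 SD in the last.

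**6. Is the unadjusted test invalid?** In 20,000 simulated trials with 44 per arm and an unrecorded covariate correlated r with the outcome, the unadjusted t-test gave:

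- r = 0.3: type I error 5.2%, power 79.8%;
- r = 0.5: type I error 5.0%, power 79.9%.

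The mean error was about 0.00 in both. ANCOVA kept the error rate (5.2% and 4.9%) and gave power of 83.0% and 89.2%. For comparison, R² = 0.20 corresponds to r = 0.45, so r = 0.5 is slightly beyond the range in the table.

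**The case against.** The strongest reply is that nothing is invalid. Imbalance in theatre treatment is random, the nominal 5% already allows for it, and late opening is a strength because it keeps theatre care independent of the arm. All of that stands.

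A reader might also infer that the imbalance could never be examined or corrected. The documents do not support this: the electronic record is to be reviewed anyway, and identifiers are kept so that further information can be retrieved during analysis. What is missing is pre-specification. That still matters, because a covariate chosen once an imbalance has been seen is a data-driven choice.

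Other points also stand in part:

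- The size rests wholly on assumptions, since no section says that any patient receives a block. At 10% use and 0.4 SD the gain is negligible.
- Procedure type and length are recorded and may partly stand in for anaesthetic technique. The R² values are for block alone, so its gain over an analysis using those variables could be smaller.
- The seven-day opioid total is diluted by days when theatre treatment no longer acts. The larger figures are relevant mainly to first-day outcomes.
- The Mann-Whitney test takes no covariate, so recording a block changes no analysis unless the method changes too.

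These limit the size of the point and shape the remedy. They do not remove the case for recording and pre-specifying a valid and potentially prognostic covariate at low cost.

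**Conclusion.** The point holds as a worthwhile, inexpensive improvement. Theatre anaesthesia and analgesia are absent from the listed parameters, no section standardises them, and no analysis is planned to use them, although they can validly be adjusted for here.

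The loss is precision and interpretability. It should not be read as bias or as an inflated error rate: the unadjusted test keeps about 5% type I error and its planned 80% power. With block use of 10% to 50% and an effect of 0.4 to 1.0 SD, both assumed, adjustment raises power to between about 81% and 88%, equivalent to between 89 and 110 patients instead of 88. Gains should be nearer the top for early VAS, first ambulation and inpatient opioid use, and small for the seven-day total. Confidence in the size is low because the documents give neither input.

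**What to change.** Make no change to anaesthetic care. Before unblinded data are examined:

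1. Add to Study Parameters, from the anaesthetic record: neuraxial or regional block (yes/no), wound infiltration (yes/no) and total intraoperative opioid in morphine equivalents. Limit all three to treatment given before the envelope is opened, and record the opening time so that the limit can be applied.
2. Tabulate the three variables by arm.
3. Pre-specify block (yes/no) as a covariate or stratum in the VAS, first-ambulation and opioid comparisons. Use ANCOVA or, if the outcome is skewed, a stratified rank test or a model on a transformed scale. Report the unadjusted result alongside.
4. State when post-operative opioid counting starts, so that intraoperative opioid is used as a covariate and is not also counted in the outcome.

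**Cost.** Three chart fields and one time per patient, largely within the record review already planned, plus one covariate or stratum and a method that can take it. The downside is slightly more abstraction, for little return on the seven-day total if few patients receive a block.

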Elastic binders that surround the abdomen are commonly used after laparotomy and laparoscopic abdominal surgery with the aim of improving postoperative discomfort and pain, aiding in respiratory function, enhancing early mobilization, and decreasing seroma formation (3-5). While abdominal binder use has been studied after cesarean delivery, ventral hernia repair, and laparotomy for major abdominal surgery, its use has not been well studying in gynecology. Szender, et al., found that the use of an abdominal binder was well-tolerated and was relatively inexpensive and to increase ambulation after gynecologic surgery. However, the study did not find a statistically significant decrease in narcotic use (6). Additionally, the true effect of postoperative abdominal binder use on pain is unclear. Multiple studies have found improved pain scores, but there has been little data to correlate pain scores with actual postoperative narcotic usage. The aim of this study is to assess the effect of abdominal binder use on total postoperative narcotic use within seven days following pelvic surgery.

Objectives:

Primary objective: To assess the effect of abdominal binder use on total post-operative narcotic use within seven days following pelvic surgery.

Secondary objectives: To assess whether the use of an abdominal binder shortens the time to first ambulation after surgery.

Aims:

1. Determine postoperative total narcotic usage within the first seven days after pelvic surgery in patients who do not use an abdominal binder versus those who do use an abdominal binder.
2. Compare postoperative pain scores in postoperative patients with and without abdominal binder usage.
3. Compare length of time to first ambulation in postoperative patients with and without abdominal binder usage.
4. Describe associations between abdominal binder use and demographic data, medical comorbidities, indication for procedure, type of procedure, and perioperative/postoperative complications.

Hypothesis: Abdominal binder use will lead to improved postoperative pain scores, less total narcotic usage within seven days of surgery, and shorter time to first ambulation after surgery.

Patient selection:

Inclusion criteria

- Patients must be 18 years or older as well as willing and able to provide informed consent
- Patients undergoing going a scheduled pelvic surgery with plan to be admitted overnight (at least one night) after surgery.

Exclusion criteria

- Patients younger than 18 years old

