On discharge, patients randomized to the abdominal binder arm will be instructed to wear the binder while awake each day during the first seven days after surgery. Once the patient is more than seven days post-surgery, she may continue to wear the binder as much as she would like.

It will be discussed at the time of discharge that patients should expect a follow up phone call from a study investigator on post-operative day 7. All patients enrolled in the study will be contacted by phone by a study investigator on postoperative day seven regarding post-operative narcotic use (i.e. the number of remaining narcotic pills they have) and to give an estimate (percentage) of the amount of time the abdominal binder was worn during the first seven days. Study investigators will later review the patients' EMR to determine the quantity of narcotics they were discharged home with and calculate the total usage based on what the patient communicated on POD#7.

Patients will then continue to follow with their primary surgeon as scheduled for post-surgical follow up.

Alternatives to participation:

Subject participation in this study is voluntary. Subjects can refuse to participate or withdrawal at any time without stating a reason. Non-enrollment or withdrawal from the study will not affect their access to medical care of which they would otherwise be entitled.

Withdrawal from study participation:

There are no medical contraindications to binder use aside from a large wound that is left open to heal.

Withdrawal from the study is based on patient preference. Subjects may withdrawal at any time without stating a reason. Patients who withdrawal will remain included in the study as part of the "intention-to-treat" principle. If it is discovered that they did not give an accurate medical history or did not follow instructions for the study given by the study doctor and/or study nurse, the subject may be taken off the study at any time. Information that has already been collected will continue to be retained

Adverse Event Monitoring and Reporting:

This study will utilize the Common Terminology Criteria for Adverse Events (CTCAE) v4.03 for adverse event monitoring and reporting. The CTCAE v4.03 can be accessed from the CTEP homepage (<http://ctep.cancer.gov>). All appropriate treatment areas will have access to a copy of the CTCAE v4.03.

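### Outpatient narcotic use is taken from the EMR dispense number and pills remaining, with no fill question, so an unfilled prescription with zero pills left can score as fully taken

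*Combined protocol and SAP*

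**What the plan says.** The Background and Rationale section gives the aim of the trial as "to assess the effect of abdominal binder use on total postoperative narcotic use within seven days following pelvic surgery". Under Study Parameters, total use in morphine equivalents "will be calculated based on inpatient usage and outpatient usage". The outpatient part comes from phoning the patient on postoperative day 7, "asking how many narcotic pills they have remaining and then comparing that to what the EMR shows the narcotic prescription dispense number".

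The section After discharge home describes the same step. It specifies the narcotic item of the call as "i.e. the number of remaining narcotic pills they have". The only other item named is a request "to give an estimate (percentage) of the amount of time the abdominal binder was worn during the first seven days". Investigators later go to the EMR to "determine the quantity of narcotics they were discharged home with and calculate the total usage based on what the patient communicated on POD#7".

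So the starting quantity is described in two ways: a prescription dispense number in one section, and what the patient left hospital with in the other. Neither is defined as pills prescribed or as pills received. No section lists a fill question, a direct count of pills taken, a pharmacy check, or a scoring rule for an unfilled prescription.

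**The concern.** Pills remaining is informative about use only if the number of pills the patient started with is known. If the EMR figure is the quantity prescribed, a patient who never collected the prescription has none left, just like a patient who took them all. A person with no outpatient use from that prescription is then placed at the top of the scale, in the primary outcome.

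The written order of events offers no check. The EMR is reviewed after the call, so the caller need not know the prescribed quantity when the patient says zero, and nothing prompts a follow-up question. Data / Record Keeping retains identifiers so that charts can be consulted again during analysis, but nothing says that the chart will show whether a prescription was filled.

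The effect on the comparison depends on how non-filling is spread across the arms. If it is equal, with the same prescription size and the same share recorded as zero, variance rises but the mean difference is not biased. If it is unequal, the difference is biased. When the binder truly lowers use, the bias is towards zero if binder patients fill less often and away from zero if they fill more often.

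**Working it through.** **1. The rule applied to each fill state.** Let Q be the EMR quantity and R the pills reported remaining, and read the comparison as Q - R.

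| Patient | True use | R | Score |
|---|---|---|---|
| Filled, took all | Q | 0 | Q |
| Filled, took none | 0 | Q | 0 |
| Never filled, answers zero | 0 | 0 | Q |

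The first and third patients cannot be told apart from the data listed. The error for the third is the whole prescription. The second is scored correctly, and the inpatient component is unaffected.

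**2. The plan's own figure.** Statistical Considerations states that "a total of 88 patients (44 in each arm) would be required to achieve a power of 80% with an alpha error of 0.05", but gives no target difference and no SD, so the figure cannot be reproduced. Solving backwards, a two-sided two-sample t-test with 44 per arm, alpha 0.05 and 80% power detects a standardized difference of 0.604. The normal approximation gives (1.960 + 0.842) × √(2/44) = 0.597.

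**3. Bias in closed form.** Let pB and pC be the non-fill shares in the binder and control arms, and s the share of non-fillers recorded as zero remaining, with Q and s the same in both arms. Then:

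bias (binder minus control, pills) = (pB - pC) × Q × s

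- One mis-scored patient moves the mean of an arm of 44 by Q/44, which is 10/44 = 0.23, 20/44 = 0.45 or 30/44 = 0.68 pills.
- With pC = 5%, pB = 10% and Q = 20, the bias is 0.05 × 20 × s = 1.00 × s, that is +0.10, +0.25, +0.50 or +1.00 pills at s = 0.10, 0.25, 0.5 or 1. Swapping the shares reverses the sign.
- Over Q = 10 to 30 and s = 0.10 to 1, the bias is 0.02 to 0.60 pills at 2%/4% and 0.05 to 1.50 pills at 5%/10% (control/binder).

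**4. Effect on power, as an illustration only.** Every input is assumed:
- 44 per arm and Q = 20.
- Pills used among fillers are beta-binomial (concentration 3, control mean 50%).
- Inpatient use is gamma (mean 40 MME, shape 2), and each pill is 7.5 MME.
- Non-fillers truly use 0 outpatient pills and are recorded as Q with probability s.
- In each scenario the binder mean is set so that the true difference is 0.604 SD.

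There were 8,000 simulated trials for the t-test (standard error about 0.5 points) and 3,000 for the Mann-Whitney test (about 0.8 points).

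| Non-fill, control/binder | s | t-test rejection, true use → recorded use |
|---|---|---|
| 5%/5% | 1 | 80% → 76% |
| 2%/4% | 0.25 | 80% → 77% |
| 2%/4% | 1 | 80% → 68% |
| 5%/10% | 0.10 | 80% → 77% |
| 5%/10% | 0.25 | 80% → 73% |
| 5%/10% | 0.5 | 80% → 64% |
| 5%/10% | 1 | 80% → 50% |
| 10%/5% | 0.25 | 80% → 83% |
| 10%/5% | 1 | 80% → 91% |

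For 5%/5% at s = 1 the Mann-Whitney test moves only from 79% to 78%. In the last row the difference goes from -29.7 to -37.2 MME, which agrees with the closed form: -1.00 pill × 7.5 = -7.5 MME. The higher rejection rate there reflects an exaggerated effect, not a better trial.

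**The case against.** The strongest reply is that the error rests on one reading of an ambiguous quantity. The wording in After discharge home can naturally mean pills in the patient's hands on leaving. On that reading nobody is a non-filler and the problem disappears. The protocol describes no dispensing before discharge, but it describes no pharmacy fill either.

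A second reply is that an investigator makes the call and use is calculated from what the patient says. Someone who never collected the pills may well say so, and a protocol is not a call script. Third, bias needs several things at once: an EMR figure that means pills prescribed, some non-filling, bare zeros recorded without comment, and a difference between arms. The protocol gives no evidence for the last three, and all the power figures are assumed. Finally, refills, disposal and leftover pills are equally unaddressed.

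Much of this stands as a limit on size. The ambiguity is real, the magnitude is unknown, and at modest inputs the loss is about three points of power. It does not remove the point. Study Parameters names the prescription's dispense number, neither section settles which quantity is meant, and a patient who volunteers that nothing was filled has no stated field or scoring rule. Without fill status, the trial could not show afterwards that the error was small.

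**Conclusion.** The concern holds. Read as a subtraction from the quantity prescribed, the outpatient rule gives a non-filler who answers zero the maximum score, and nothing in the listed data would reveal it. The error does not arise if the starting quantity means pills received, or if the patient reports not filling and that is acted on.

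The size runs from trivial to severe and cannot be fixed from the protocol. The severe end, such as 80% power falling to 50%, requires both unequal non-filling and few non-fillers saying so, and the protocol supports neither. This is a cheap improvement to the measurement of the primary outcome, not evidence that the trial would give a wrong answer. Confidence is medium, because it turns on what the EMR quantity means.

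**What to change.** - Define the starting quantity once, and use that definition in both After discharge home and Study Parameters.
- On the planned day 7 call, ask every patient in both arms, in the same words, whether the discharge prescription was filled and, if only partly, how many pills were received.
- Score use from that prescription as 0 if it was not filled. Otherwise use the EMR quantity, or the reported quantity if partly filled, minus pills remaining.
- Report the number of unfilled prescriptions by arm.

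The cost is one or two questions on a call already planned and a few REDCap fields. The sample size and the tests do not change. The drawback is more self-report from patients who know their arm (under Randomization, "Envelopes will be opened and allocation revealed after the conclusion of the procedure"), on a call that also asks about binder wear, so reporting error could differ by arm. The outcome already relies on self-report from the same patients, and the EMR quantity stays the starting point for those who filled in full.
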